6.2 Parts A and B Combined

The primary endpoint will be summarized by treatment sequence and visit, using the mITT analysis set. All secondary endpoints will be summarized by treatment sequence and visit, using the ITT analysis set. In addition to all summary statistics listed in section 3 above, the 95% confidence intervals for the mean response will be provided.

A plot of the mean concentration of each endpoint over time, along with 95% CI for mean, will be presented by treatment sequence.

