Encouraged by these results and taking into account that ABvac40 is an active vaccine directed specifically against the A β -40 peptide, a cross-over for the subjects receiving placebo will be offered after they complete their 18-months visit (V23), aiming to obtain additional safety data (patient-years of ABvac40 exposure) and to be able to assess its efficacy after a delayed-start. Furthermore, the long-term safety and tolerability of ABvac40 in patients receiving a booster after their Part A vaccination scheme will be assessed.

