2.6 Study Population

Patients (between 55-80 years of age) diagnosed either with a-MCI or vm-AD will be included in the trial. To ensure the primary safety and efficacy endpoints of the study a minimum of 60 subjects with a-MCI or vm-AD per treatment group (verum and placebo) are required. The amyloid-PET positive and amyloid-PET negative patients will be independently randomized following a ratio 1:1 between verum and placebo (Part A).

To ensure the primary efficacy endpoint with a potency of 85% at least 15 subjects per treatment group (verum and placebo; 30 in total) are required to complete the study. Since a total of 120 subjects will be initially included in the study and we estimate ~40% dropouts along the clinical trial, 70 are expected to complete the Part A of the protocol.

Participants in Part A will have to complete their 18-month visit (V23) in order to be eligible for the Part B of the study.

All patients who have participated in Part A, have not presented any drug reaction and have no MRI safety issues before the first immunization in Part B, could participate in Part B.

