4.1.2 Part B

All the endpoints of Part B will be explorative. No hypothesis will be tested.

Both the primary and secondary safety endpoints mentioned in Section 4.1.1 will also be evaluated in Part B (only as exploratory safety endpoints).

Regarding efficacy, the following exploratory endpoints will be evaluated:

- Presence of specific antibodies against A β 40 in plasma
- Characterization of the immune response:
 - o Level of anti-A β 40 antibodies in CSF
 - o Levels of antibody secreting cells
- Assessment of disease biomarkers:
 - o Levels of A β peptides in plasma
 - o Cortical fibrillary amyloid deposition assessed by PET scans.

- Brain volumetric and atrophy of the hippocampus using magnetic resonance imaging
- Assessment of cognition and quality of life:
 - MMSE
 - CDR scale
 - RBANS
 - ADCS-ADL MCI
 - C-SSRS
 - TMT
 - IGE
 - EQ-5D-5L

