Mixed-model repeated-measures (MMRM) analyses will be performed for all the primary and secondary efficacy variables (section 7.1) to assess between-group differences in change scores from baseline (V0/V1) to Int-6m (V16), V21 and to the final visit (V25). The dependent variable in each MMRM analysis will be “change from baseline”. Fixed effects will include baseline scores on outcome measures, age at baseline, group assignment, amyloid positivity, study visit, and treatment-by-visit interaction. Additionally, covariates that are significantly associated with the response measure ($p < 0.15$) and are out of balance at baseline ($p < 0.2$) will be included as fixed effects. Variables considered as potential covariates in each model will be demographic variables, baseline characteristics, general treatment for AD and concomitant medication.

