9.1.4 Efficacy and Safety Analysis (Part B)

The analyses for Part B will mirror the analyses of Part A, without testing any hypothesis. The detailed statistical analyses will be described in the Statistical Analysis Plan.

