2.2.2.3 Exploratory Efficacy Objective (Other)

- To assess the changes in the disease biomarkers elicited by ABvac40 in the overall study population.
- To assess the changes in cognition and quality of life elicited by ABvac40 in the overall study population and according to the treatment scheme during Part A and B.
- To assess the immunological memory, characterizing the immune response ex vivo elicited by the booster in patients who have received ABvac40 during Part A
- To assess the potential relationship between antibody titration, biomarkers and cognitive state.
- To define the optimal ABvac40 treatment scheme.

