3 GENERAL STATISTICAL CONSIDERATIONS AND REPORTING CONVENTIONS

The following general analysis and reporting conventions will be used:

- The following treatment labels will be used for presentation of results in the statistical tables:
 - Statistical testing of primary and secondary efficacy outcomes in Part A of the study and summaries of Adverse Events (AE)s across parts A and B of the study will be presented by the following treatment groups:
 - ABvac40
 - Placebo
 - Summary statistics for all other parameters (Part A and Part B, combined) will be presented by the following treatment sequences:
 - ABvac40 arm Part A / Placebo+Booster arm Part B
 - Placebo arm Part A / ABvac40 arm Part B
- Visits will be presented in outputs in terms of weeks, with a suffix of “A” or “B” to indicate the study part (e.g. Week 0A, Week 2A..... Week 0B, Week 2B, etc...).
- Only available data will be included in summary statistics and no substitutions or imputations of missing values will be performed.
- Categorical variables will be summarized using counts (n) and percentages (%) and will be presented in the form n (%). Percentages will not be presented for counts of 0, while percentages of 100 will be reported as a whole number (i.e. “100%”). All other percentages will be presented to 1 decimal place. To ensure completeness, summaries for categorical variables will include all categories, even if no patients had a response in a particular category. Denominators will include patients with non-missing data, unless otherwise specified. The number of patients with missing data for categorical variables will be summarized without a percentage.
- Continuous variables will be summarized using mean, 95% confidence interval (CI) for mean, standard deviation (SD), first quartile (Q1), third quartile (Q3), minimum, maximum, median, and number of patients. The mean, median, Q1, Q3 and CI will be rounded and reported to 1 more level of precision than the original observations, and the SD will be rounded and reported to 2 more levels of precision than the original observations. The minimum and maximum will be reported to the same precision as the original data.
- Following SAS default rules, the median will be reported as the rounded average of the two middle sorted values if the dataset contains even numbers of non-missing data.

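### SAP 6.2 defines no between-sequence difference for Part B, although the protocol has Part B mirror Part A and both documents aim to assess delayed-start efficacy; SAP 9.2 does not declare the departure

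*SAP*

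**What the plan says.** - **Protocol 9.1.4:** "The analyses for Part B will mirror the analyses of Part A, without testing any hypothesis". Details are left to the SAP. Protocol 4.1.2 sets the status: "All the endpoints of Part B will be explorative. No hypothesis will be tested".
- **What would be mirrored.** Protocol 9.1.2 plans ANCOVA on the maximal increment, descriptive analysis of the biomarker and cognition variables, and an MMRM of change from baseline for all primary and secondary efficacy variables. The MMRM fixed effects include "group assignment, amyloid positivity, study visit, and treatment-by-visit interaction".
- **Why Part B exists.** Protocol 2.2 gives as one purpose of the cross-over "to be able to assess its efficacy after a delayed-start". SAP 2.1 also names efficacy of the delayed start, and SAP 2.2.2.3 includes change in cognition and quality of life by treatment scheme across both parts.
- **What the SAP provides.** The ANCOVA and MMRM appear only under SAP 6.1, Part A. For both parts combined, SAP 6.2 says "All secondary endpoints will be summarized by treatment sequence and visit, using the ITT analysis set", adding a 95% CI for each mean and a plot by sequence. SAP 3 adds: "Only available data will be included in summary statistics and no substitutions or imputations of missing values will be performed".
- **Who reaches Part B.** Protocol 2.6 expects about 40% dropout, with 70 of 120 completing Part A. Entry requires completion of V23, and patients must "have not presented any drug reaction and have no MRI safety issues before the first immunization in Part B".
- **Declared changes.** SAP 9.2 covers analysis sets, an added outcome and variables not assayed. It does not mention the Part B method.

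**The concern.** A delayed-start extension is informative because the two sequences were randomised, so the natural quantity is the difference between them after the delayed group has been vaccinated. Under SAP 6.2 the reader gets two separate curves and has to compare them by eye.

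Those curves are unadjusted for baseline, age and the stratification factor, and the patients behind each point change along the line. Some leave in Part A. Others do not enter Part B because of a drug reaction or an MRI finding, and either could occur more often on vaccine than on placebo. At stake is whether Part B can address its own exploratory question with a prespecified estimate, or whether visit, covariates and population will be chosen after the data are seen. The Part A primary analysis is not affected.

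**Working it through.** **1. The plan's own figures.** With SDs 2.0 and 1.0, the average variance is (4 + 1)/2 = 2.5. For a difference of 1.778, one-sided 0.025 and 85% power, n = 2 × 2.5 × (1.960 + 1.036)² / 1.778² = 14.2, so 15 per group, as Protocol 2.6 states. Power at 35 per group is 99.6%. Expected completers are 120 × 0.60 = 72; the stated 70 means a loss of 50/120 = 41.7%. These figures reproduce, but they concern the Part A primary endpoint. Neither document gives a precision or power figure for Part B.

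**2. The texts side by side.**

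| Element | Part A (SAP 6.1) | Parts A and B (SAP 6.2) |
|---|---|---|
| Model | ANCOVA, MMRM | none |
| Adjustment | baseline, age, a-PET status (MMRM) | none |
| Between-group difference with 95% CI | at each visit (MMRM) | none |
| Missing data | likelihood-based (MMRM) | available cases |

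Two details suggest that the gap may be unintended. SAP 6.1.3 cites an MMRM described in section 6.2, but 6.2 contains none; the model is in 6.1.2. SAP 3.1.4 speaks of analysing cognition over both parts, and no method beyond 6.2 is given.

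**3. Precision of the missing quantity, in SD units.** With 35 per sequence, each mean has a 95% CI half-width of t(34)/√35 = 0.34, and an unadjusted difference t(68) × √(2/35) = 0.48. With 25 per sequence the values are 0.41 and 0.57. The 35 is half of the 70 expected Part A completers; the 25 is an assumption for further loss.

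**4. What selection could do (assumed inputs only).** Six visits, unit-variance change scores with equal correlation r, 100,000 simulated patients per sequence, and dropout depending on the last observed value with a logit slope of 1 per SD unless stated. Last-visit results for available-case means, in SD:

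| Dropout scenario | Result shown | r = 0.4 | r = 0.6 | r = 0.8 |
|---|---|---|---|---|
| 40% in both, same mechanism | shift in each mean | 0.17 | 0.25 | 0.32 |
| 40% in both, same mechanism | bias in difference | about 0 | about 0 | about 0 |
| 40% in both, slope 0.5 v 1 | bias in difference | 0.07 | 0.11 | 0.14 |
| 30% v 50% | bias in difference | 0.10 | 0.14 | 0.18 |
| 40% completely at random | bias in difference | about 0 | about 0 | about 0 |

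A likelihood estimate of the MMRM type moved by less than 0.01 SD throughout. That is expected, because the simulated loss depended only on observed values.

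**5. A bound on one mean.** If the worst 40% on a variable correlated ρ with the outcome all left, the shift is ρ × φ(0.253)/0.60 = 0.64ρ, or 0.19 to 0.45 SD for ρ from 0.3 to 0.7.

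**The case against.** **The protocol does not name a Part B model.** It says mirror, excludes testing, makes Part B exploratory and leaves the detail to the SAP, which takes primacy over it. Description is also part of what Part A does. This stands as far as p-values go: their absence is as planned. It does not explain why the estimation half of Part A is missing, or why 9.2 is silent.

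**Each sequence's mean and CI is planned, so an unadjusted difference can be reconstructed.** True: √(0.34² + 0.34²) gives about 0.49 SD, close to the 0.48 above. But it would be an available-case figure without covariate adjustment, and nobody has committed to it.

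**Same-patient output already exists.** SAP 3.1.3 and 3.1.4 repeat the combined outputs in patients who are in the per-protocol sets of both parts. Those sets require all doses and attendance at V20 and V20B, so the curves follow largely the same patients. This stands, and a further descriptive plot in Part B entrants adds little. The sets are narrower than all entrants and still yield no difference.

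**The contrast is not a pure early-start effect.** The ABvac40-first sequence receives a further ABvac40 dose at V13B, before V16B, V21B and V22B. This stands and must be stated with the result.

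**Modelling every visit is impractical.** This stands. The 22 post-baseline blood visits would need 22 × 23/2 = 253 unstructured covariance parameters for about 120 patients. The seven cognition visits need 7 × 8/2 = 28.

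**Conclusion.** SAP 6.2 omits any between-sequence estimate for Part B, and 9.2 does not declare the omission. This follows from the texts and needs no assumption. It is an inexpensive improvement to an exploratory part of the trial, not a threat to the primary result.

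The selection argument is a risk only. On the assumed inputs, a sequence mean could shift by 0.17 to 0.32 SD, against a CI half-width of 0.34 SD. The difference could be biased by anything from about 0 to 0.18 SD. With no dropout mechanism in the documents, neither size nor direction can be predicted.

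Three stronger readings are not supported:

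- A reader might infer that the Part B curves are distorted. They may be. If loss is completely at random there is no shift, and if it acts alike in both sequences the difference is nearly unbiased even though each mean moves.
- A reader might expect a spurious cognitive step at Week 0B. Protocol 7.2.1.3 schedules the Part B battery only at V16B, V21B and V22B, so no such point exists.
- A reader might say that 9.2 should also declare a dropped analysis for the objective "To assess the potential relationship between antibody titration, biomarkers and cognitive state". The SAP has no analysis for it, but Protocol section 9 specified none either, so there was nothing to declare.

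**What to change.** In SAP 6.2, using the ITT set:

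1. Add an exploratory MMRM by randomised sequence for the continuous secondary endpoints, with the Part A covariates (baseline as in 6.1.3, age, a-PET status), visit and sequence-by-visit.
2. Restrict it to the visits where each endpoint is measured. For cognition these are V16, V21, V23, V25, V16B, V21B and V22B (IGE is not done at V23). For PET, CSF and EQ-5D-5L they are V21, V25 and V21B. For plasma endpoints, name a short list of visits in advance.
3. Report LS means and the between-sequence difference with 95% CI at the Part B visits, without p-values.
4. State that the contrast compares whole sequences, including the V13B booster in the ABvac40-first group, and that the model corrects only for loss explained by observed data. Exclusion for a drug reaction or MRI finding is covered only to that extent.
5. Record the Part B method in 9.2. If the sponsor prefers description alone, say there that no delayed-start effect is estimated.
6. Correct the cross-reference in 6.1.3 to 6.1.2.

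A table comparing patients who did and did not enter Part B, by arm, would help readers judge selection. A regression of biomarkers and cognition on antibody response is optional.

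Cost: SAP text, modest programming on data already collected with a model already coded for Part A, and somewhat more exploratory output.

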7 SUMMARY OF SAFETY ASSESSMENTS

All summaries will be presented using the Safety Analysis Set.

7.1 Study Treatment Compliance

Percentage compliance to study drug administration will be calculated as:

% Compliance = (Number of doses of study drug taken in Part A * 100) / 6, rounded to 1 decimal place, where 6 = number of planned doses for Part A

% Compliance = (Number of doses of study drug taken in Part B * 100) / 6, rounded to 1 decimal place,

where 6 = number of planned doses for Part B

Compliance will further be categorized into the following groups: (<80%, \geq 80% to 100%).

Summaries of the calculated compliance and the categorized compliance will be presented by treatment sequence and study part. The denominator for the percent of patients within each compliance category will be the number of patients in the safety analysis set who entered the specific study part. A listing of study treatment compliance will also be presented.

7.2 Summary of Primary Safety Outcome

7.2.1 Adverse Events

Adverse events will be classified as Treatment-Emergent AEs (TEAEs) or non-Treatment-Emergent AEs (non-TEAEs), based on the comparison of the AE onset date/time with the start date/time of study treatment.

- A TEAE will be defined as an AE which starts or worsens in severity during or after the first administration of study treatment.
- A non-TEAE will be defined as an AE which starts or worsens in severity prior to the start of the first administration of study treatment.

The following algorithm will be used to identify the treatment group under which each AE will be summarized:

For SAESIs:

- AEs that start or worsen in severity at any time after a patient's first dose of ABvac40 will be associated with the ABvac40 treatment group.
- AEs that start or worsen in severity after first dose of Placebo, but before first dose of ABvac40, will be associated with the Placebo treatment group

For non-SAESIs:

- For patients randomised to the ABvac40 arm Part A / Placebo+Booster arm Part B treatment sequence:
 - AEs that start or worsen in severity at any time during or after a patient's first dose of study drug in part A and prior to their booster ABvac40 vaccination will be associated with the treatment received at their last injection prior to the AE.
 - AEs that start or worsen in severity during or after a patient's booster ABvac40 vaccination will be associated with the ABvac40 treatment group.
- For patients randomised to the Placebo arm Part A / ABvac40 arm Part B treatment sequence:
 - AEs will be associated with the treatment received at their last injection prior to the AE.

For the purposes of classifying AEs as treatment emergent and to assign treatment groups, partial AE start and end dates will be imputed to allow comparison with the study treatment date start and end dates. Section 9.1.1 below presents the imputation rules. Note, the imputed dates will be used for classification purposes and treatment group assignment purposes only and the original partial AE dates will be presented in data listings.

An overall summary of AEs will be presented by treatment group, by providing counts and percentages of patients with any: TEAE, non-TEAE, Treatment related TEAEs, TEAE leading to treatment discontinuation, TEAEs leading to death, Treatment-Emergent Serious AE (TESAE), Treatment-

Emergent SAESIs, Treatment related TESAEs, TESAEs leading to treatment discontinuation and TESAEs leading to death.

Counts and percentages of patients will be presented by treatment group, SOC and PT for the following: TEAEs, non-TEAEs, TEAEs leading to study withdrawal, Treatment-Emergent SAESIs and TESAEs.

Counts and percentages of patients with TEAEs will be presented by treatment group, SOC, PT and maximum causality.

Counts and percentages of patients with TEAEs will be presented by treatment group, SOC, PT and maximum severity.

For summaries by maximum causality/severity, if a patient reported more than one AE with the same PT, the AE with the maximum causality/severity will be presented. If the causality/severity of an AE is missing, the causality/severity will be treated as missing in summaries. If a patient reported more than one AE within the same SOC, the patient will be counted only once under the maximum causality/severity within the SOC.

The denominator for the percentages for the ABvac40 group will be all patients in both the ABvac40 arm Part A / Placebo+Booster arm Part B and Placebo arm Part A / ABvac40 arm Part B treatment sequences who took at least one dose of ABvac40 throughout the study.

The denominator for the percentages for the Placebo group will be all patients in both the ABvac40 group Part A / Booster group Part B and the Placebo arm Part A / ABvac40 arm Part B treatment sequence who took at least one dose of Placebo.

In Part B, the safety population will be those subjects who received at least one dose.

AEs will be listed by treatment group and patient identifier. In addition, patients with SAEs and AEs leading to premature discontinuation of treatment period from the study will be individually listed.

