3.2.1 Exploratory Safety Objective

- To evaluate the safety and tolerability of repeated doses of ABvac40 after delayed start in patients receiving placebo during Part A, and the long-term safety and tolerability of ABvac40 in patients receiving a booster after their Part A vaccination scheme.

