4.4 Study Treatments

4.4.1 Treatments to Be Administered

The treatments to be administered are verum (ABvac40) and placebo (ABvac40 vehicle without its active ingredient).

The following table shows when the vaccination will occur:

Table 6: Treatment Time points

#	Treatment visits	Week #	Month #
Part A			
1	V1	0	0
2	V4	4	1
3	V7	8	2
4	V10	12	3
5	V13	16	4
6	V18*	42	10

Part B			
1	V1B [†]	0	0
2	V4B [†]	4	1
3	V7B [†]	8	2
4	V10B [†]	12	3
5	V13B [†]	16	4
6	V18B [†]	42	10

* All patients who will attend their V18 after April 2020 must be tested for COVID-19 by PCR method before receiving the study medication. A specific ICF must be signed by the applicable patients authorizing this test (see Section 6.1.1.1 for further details)

[†] All patients must be tested for COVID-19 during the Part B vaccination visits before receiving the study medication (see Section 6.1.1.2 for further details)

Verum

Name: ABvac40

Active ingredient: Conjugated A β x-40 to KLH

Vehicle: Phosphate buffer containing 0.35% aluminium hydroxide (adjuvant)

Pharmaceutical Form: Injection ready vials

Posology: Part A: Verum group: Six administrations: the first five administered once every 4 weeks (28 \pm 3 days) and the sixth at week 42 (V18), 26 weeks after the fifth. Each administration consists of 1 mL injection of ABvac40 (containing 0.2 mg of Abetax-40).

Part B: Delayed start group: Six administrations: the first five administered once every 4 weeks (28 \pm 3 days) and the sixth at week 42 (V18B), 26 weeks after the fifth immunization. Booster group: One administration at week 16 (V13B).

Each administration consists of 1mL injection of ABvac40 (containing 0.2 mg of Abetax-40).

Method of administration: Subcutaneous injection.

Placebo

Name: Placebo

Active ingredient: Nil

Vehicle: Phosphate buffer containing 0.35% aluminium hydroxide (adjuvant)

Pharmaceutical Form: Injection ready vials

Posology: Part A: Placebo group: Six administrations: the first five administered once every 4 weeks (28 \pm 3 days) and the sixth at week 42 (V18), 26 weeks after the fifth. Each administration consists of 1mL injection of ABvac40 vehicle.

Part B: Booster group: Five administrations: the first four administered once every 4 weeks (28±3 days) and the fifth at week 42 (V18B), 30 weeks after the forth. Each administration consists of 1mL injection of ABvac40 vehicle.

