2.1.2 Part B

Part B of the study will last for 18 months (from V1B to V22B). The scheme of visits will mirror the Part A scheme. The first visit of Part B (V1B) will take place at least 18 months after the patient started Part A (i.e., patient should have completed V23 which is month 18 of Part A to enter Part B). The study scheme for Part B is shown in also included in Figure 2.

The patients randomized to the placebo group during Part A will receive five monthly (every four weeks) immunizations with ABvac40 plus a booster shot after 6 months (Placebo arm Part A / ABvac40 arm Part B), whereas the patients randomized to the ABvac40 group during Part A will receive placebo following this schedule, except in V13B (Week 16), where they will receive an ABvac40 booster shot (ABvac40 arm Part A / Placebo+Booster arm Part B). Given the extended inclusion period of Part A, the V13B booster will take place at different timepoints relative to the patients' last immunization.

Figure 2: AB1601 Study Schematic – Part B

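### In the pooled Part A+B adverse event tables, patients already vaccinated with ABvac40 are counted under Placebo from V1B until the V13B booster, so the Placebo column is not vaccine-naive

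*SAP*

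**What the plan says.** SAP section 3 presents adverse event summaries across Parts A and B in two columns, ABvac40 and Placebo. SAP 7.2.1 then sets the column for each event.

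- **Non-SAESIs, ABvac40-first sequence, before the booster:** events from the first Part A dose and "prior to their booster ABvac40 vaccination will be associated with the treatment received at their last injection prior to the AE".
- **Non-SAESIs, same sequence, from the booster on:** events "during or after a patient's booster ABvac40 vaccination will be associated with the ABvac40 treatment group".
- **SAESIs (ARIA and aseptic meningo-encephalo-myelitis):** events starting or worsening "at any time after a patient's first dose of ABvac40 will be associated with the ABvac40 treatment group".

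On dosing, Protocol 4.4.1 gives "Part A: Verum group: Six administrations: the first five administered once every 4 weeks", with the sixth at week 42 (V18). In Part B, SAP 2.1.2 says these patients "will receive placebo following this schedule, except in V13B (Week 16), where they will receive an ABvac40 booster shot".

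Under SAP 7.2.1 the Placebo denominator is everyone in either sequence who took at least one placebo dose. It therefore includes ABvac40-first patients once they are injected at V1B.

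**The concern.** The section makes two different assumptions about how long vaccination matters. For SAESIs, and for any event after the seventh dose, an ABvac40 dose counts from then on, even after the V18B placebo injection. For other events after the first six doses, a single vehicle injection ends the attribution. The SAP offers no washout argument, and SAP 9.2 does not list the rule among the changes to protocol-specified analyses.

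The protocol does not treat the vaccine as short-acting. Its Part B safety objective includes "the long-term safety and tolerability of ABvac40 in patients receiving a booster after their Part A vaccination scheme", immunological memory is an objective (Protocol 3.2.2.2), and Protocol 8.3.9 asks for related SAEs more than 14 months after the last dose to be reported. A late reaction during V1B to V13B, even one the investigator judged related, would appear as a treatment-related event under Placebo. The comparator column of the combined safety tables would then mix vaccine-naive and vaccinated patients, and no adverse event table by sequence or for Part A alone is specified that would separate them.

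**Working it through.** **Inputs.** V18 is at week 42, V23 at week 77 and V25 at week 104; V1B to V13B is 112 days, or 16 weeks (Protocol synopsis, study schemes). There are 60 patients per group and about 70 of 120 completers (SAP 3.2). The number of ABvac40-first patients entering Part B is not given; I take 35 (half of 70) to 60 (all).

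**1. The plan's own figure.** SAP 3.2 wants more than 95% probability of seeing an event with a 5% rate among 60 patients: 1 − 0.95^60 = 95.4%. It reproduces, but says nothing about attribution.

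**2. Which column an event falls in, for an ABvac40-first patient dosed as planned**

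| Event | Last injection | Column |
|---|---|---|
| Non-SAESI, first dose to V1B | ABvac40 | ABvac40 |
| Non-SAESI, V1B to V13B | placebo | **Placebo** |
| Non-SAESI, V13B to V18B | ABvac40 | ABvac40 |
| Non-SAESI, after V18B | placebo | ABvac40 |
| SAESI, any time after first dose | either | ABvac40 |

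Rows 2 and 4 have the same last injection and different columns.

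**3. When the window falls.** It opens 77 − 42 = 35 to 104 − 42 = 62 weeks after V18 and closes 16 weeks later, at 51 to 78 weeks. That is about 12 to 18 months, which agrees with the synopsis grouping of booster timing. These are nominal times: Part B starts at least 18 months after Part A started, and SAP 2.1.2 states no maximum. If V13B is not given, placebo attribution has no end; Protocol 6.1.1.2 has Part B doses skipped when a COVID-19 delay exceeds one month.

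**4. Share of the Placebo column by headcount.** 35/(60 + 35) = 36.8%; 60/(60 + 60) = 50%.

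**5. Share by person-time**, if 60 placebo patients are each followed 77 to 104 weeks in Part A:

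- 35 entrants: 35×16 = 560 person-weeks. 560/(60×77 + 560) = 10.8%; 560/(60×104 + 560) = 8.2%.
- 60 entrants: 60×16 = 960 person-weeks. 960/(60×77 + 960) = 17.2%; 960/(60×104 + 960) = 13.3%.

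Dropout from Part A placebo would raise these shares.

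**6. Chance that a late event lands under Placebo.** Assume a 5% risk per patient in the window. Then the chance of at least one is 1 − 0.95^35 = 83% or 1 − 0.95^60 = 95%.

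**7. Effect on the Placebo percentage.** Let b be the 77-week background incidence in vaccine-naive placebo patients, with constant hazard, and keep the assumed 5% late risk. Background over 16 weeks is q = 1 − (1 − b)^(16/77). The window risk is r = 1 − (1 − q)(0.95). With m entrants, the printed percentage is (60b + m·r)/(60 + m).

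| b | r | m = 35 | m = 60 | Vaccine-naive only |
|---|---|---|---|---|
| 0% | 5.0% | 1.75/95 = 1.8% | 3/120 = 2.5% | 0% |
| 5% | 6.0% | (3 + 2.10)/95 = 5.4% | (3 + 3.60)/120 = 5.5% | 5.0% |
| 10% | 7.1% | (6 + 2.47)/95 = 8.9% | (6 + 4.23)/120 = 8.5% | 10.0% |

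For rarer events the Placebo percentage rises. At 10% background it falls, because the added patients are at risk for only 16 weeks.

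**The case against.** The strongest reply is that little of importance is touched. The confirmatory safety analysis belongs to Part A and is descriptive (Protocol 9.1.3.1); Part B tests no hypothesis (Protocol 4.1.2). Part A is locked before Part A results are reported (SAP 2.3). Within Part A each patient's planned injections are all the same treatment, so the last-injection rule moves nothing. The prespecified events of special interest always stay under ABvac40. Adverse events are listed by patient, and examinations, vital signs, ECG and laboratory data are summarised by sequence. All of this stands and limits the reach of the point to the pooled tables. It does not explain why those tables put vaccinated patients in the comparator; listings let a reader trace an event but do not correct a column.

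One could also read the booster in SAP 7.2.1 as the Part A dose at V18, which would remove the problem for patients who received it. That reading is weak. Before V18 this arm is scheduled only ABvac40, so a last-injection rule would do nothing, and SAP 2.1.2 and the Placebo+Booster label both point to V13B. The section does leave the visit unnamed.

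A reader might infer that the rule always favours the vaccine. The documents do not support that: the event itself moves in one direction, but the percentage need not, as step 7 shows. Nor does each such event necessarily lower the ABvac40 count. The tables count patients, and someone already counted under ABvac40 for the same preferred term stays there.

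**Conclusion.** The point holds for the pooled Part A+B tables of non-SAESIs and should be fixed. Read with V13B as the booster, SAP 7.2.1 counts 16 weeks of events in previously vaccinated patients as Placebo events, against the logic the same section applies elsewhere and without a stated reason. Those patients are 37% to 50% of the Placebo denominator under the assumed 35 to 60 entrants, but about 8% to 17% of its person-time if Part A follow-up is complete.

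It would go too far to conclude that the Part A safety result is compromised, or that late vaccine effects are being hidden. Tables limited to Part A data contain none of these events, and nothing in the documents shows that late effects exist. The 5% late risk and the background rates above are illustrations. The finding is about where a late event would be counted, and that the resulting Placebo percentage cannot be read as a vaccine-naive rate.

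**What to change.** In SAP 7.2.1, before the combined Part A and B lock:

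1. Show non-SAESIs from V1B to V13B in the ABvac40-first sequence in a separate column, such as *placebo after ABvac40*, with its own denominator. Alternatively, assign them to ABvac40 under the SAP's existing SAESI rule.
2. Restrict the Placebo denominator to vaccine-naive placebo patients. Changing attribution alone would create a new error: with 35 entrants, 6 of 60 vaccine-naive patients with an event (10%) would print as 6/95 = 6.3%.
3. Name V13B as the booster in the attribution rule, and say how events are assigned when V13B is not given.
4. Present adverse events for Part A by treatment group and for Part B by sequence. Add exposure-adjusted rates, because follow-up differs between columns: if all events after the first dose go to ABvac40, that column can cover up to the 36 to 42 months of total participation, against 18 to 24 months of Part A placebo.

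The cost is a few SAP edits and some extra adverse event programming, with no new data. The Placebo column becomes smaller, at 60 patients instead of 95 to 120 under the assumptions above.
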